8.3 ADVERSE EVENTS AND SERIOUS ADVERSE EVENTS

8.3.1 DEFINITION OF ADVERSE EVENTS (AE)

AE means any untoward medical occurrence associated with the use of an intervention in humans, whether or not considered intervention-related.

8.3.2 DEFINITION OF SERIOUS ADVERSE EVENTS (SAE)

An AE or suspected adverse reaction is considered "serious" if, in the view of either the investigator or sponsor, it results in any of the following outcomes: death, a life-threatening adverse event, inpatient hospitalization or prolongation of existing hospitalization, a persistent or significant incapacity or substantial disruption of the ability to conduct normal life functions, or a congenital anomaly/birth defect. Important medical events that may not result in death, be life-threatening, or require hospitalization may be considered serious when, based upon appropriate medical judgment, they may jeopardize the participant and may require medical or surgical intervention to prevent one of the outcomes listed in this definition. Examples of such medical events include severe hypoglycemia requiring intensive treatment in an emergency room or at home, hypotension, and electrolyte abnormalities.

8.3.3 CLASSIFICATION OF AN ADVERSE EVENT

8.3.3.1 SEVERITY OF EVENT

The following guidelines will be used to describe severity of AEs that the study team learns about outside of the passive surveillance system.

- **Mild** – Events require minimal or no treatment and do not interfere with the participant's daily activities.
- **Moderate** – Events result in a low level of inconvenience or concern with the therapeutic measures. Moderate events may cause some interference with functioning.

- **Severe** – Events interrupt a participant’s usual daily activity and may require systemic drug therapy or other treatment. Severe events are usually potentially life-threatening or incapacitating. Of note, the term “severe” does not necessarily equate to “serious”.

8.3.3.2 RELATIONSHIP TO STUDY INTERVENTION

AEs that the study team learns about outside of the passive surveillance system will have their relationship to study intervention assessed by the clinician who examines and evaluates the situation based on temporal relationship and his/her clinical judgment. The degree of certainty about causality will be graded using the categories below.

- **Related** – The AE is known to occur with the study intervention, there is a reasonable possibility that the study intervention caused the AE, or there is a temporal relationship between the study intervention and event. Reasonable possibility means that there is evidence to suggest a causal relationship between the study intervention and the AE.
- **Not Related** – There is not a reasonable possibility that the administration of the study intervention caused the event, there is no temporal relationship between the study intervention and event onset, or an alternate etiology has been established.

8.3.3.3 EXPECTEDNESS

An AE will be considered unexpected if the nature, severity, or frequency of the event is not consistent with the risk information previously described for the study intervention.

8.3.4 TIME PERIOD AND FREQUENCY FOR EVENT ASSESSMENT AND FOLLOW-UP

We accessed the electronic health records and administrative data of all patients who accrued to this pragmatic trial in the course of preparing for regularly scheduled data safety monitoring meetings. We extracted data elements that documented the occurrence of any of the safety events (e.g., diagnosis codes, laboratory value, admission records) between 12 months prior to each accrued patient’s index visit and 18 months after the index visit of the last-accrued patient. The rates at which each event occurred (e.g., events per 100 patient-years) were calculated in the pre- and post-index periods by randomized treatment group so that differential changes in event rates might be observed. Event rate summaries were presented at data safety monitoring meetings approximately thrice-yearly. By their very nature, the occurrence of these safety events had been documented by health care professionals in the course of delivering timely treatment and appropriate follow-up to the accrued patients.

The occurrence of an AE or serious adverse event (SAE) may also come to the attention of project team members during patient and provider survey results. These AEs not meeting the criteria for SAEs will be captured on the appropriate report forms. Information to be collected includes event description, time of onset, clinician’s assessment of severity, relationship to study procedures (assessed only by those with the training and authority to make a diagnosis), and time of resolution/stabilization of the event. All AEs occurring while on study will be documented appropriately regardless of relationship. All AEs will be followed to adequate resolution.

Changes in the severity of an AE will be documented to allow an assessment of the duration of the event at each level of severity. AEs characterized as intermittent require documentation of onset and duration of each episode.

The project manager, in collaboration with the PI will record all reportable events with start dates occurring any time after inclusion into the study population until 7 (for non-serious AEs) or 30 days (for SAEs) after the last day of study participation. Events will be followed for outcome information until resolution or stabilization.

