7 STUDY INTERVENTION DISCONTINUATION AND PARTICIPANT DISCONTINUATION/WITHDRAWAL

7.1 DISCONTINUATION OF STUDY INTERVENTION

This minimal risk study did not include specific halting rules. The CDS suggestions were evidence-based and guideline driven and providers are always advised to exercise their clinical judgement with any CDS suggestions. However, safety monitoring meetings were held regularly to assess frequency of possible adverse events related to overtreatment (severe hypoglycemia, documented hypotension, abnormal potassium values, etc.) in all randomized clinics.

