7.3 LOST TO FOLLOW-UP

Unless they opted out of research, all patients who met study eligibility criteria and had an index visit in the accrual period were eligible for inclusion in the analysis; inclusion in specific outcome analyses varied by the clinical care gaps that were present at the index visit.

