9.4.4 SAFETY ANALYSES

Trends in safety concerns for subjects will also be followed as indicated by the Data Safety and Monitoring plan outlined in the safety oversight section below.

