channels using pharmacotherapies openly available in medical group formularies for FDA-approved indications only. Each study PCP has complete freedom to treat or not treat a given patient with whatever therapy the physician believes is best for that patient. Adverse-events information will be monitored using EHR data at a frequency determined by the safety officer and may include identification of electrolyte abnormalities and emergency department or hospital admissions related to syncope, hypotension, or hypoglycemia. Rates of monitored events will be compared in intervention and usual care clinics, and any significant differences will be promptly reported in writing to the NIH and to the HealthPartners IRB, consistent with NIH and HealthPartners IRB policy. We have budgeted funds for the safety officer but have not recruited a specific individual for this position. Consistent with NIH and HealthPartners Institute policy, the Safety Officer will not be affiliated with HealthPartners, HPMG, or PN.

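### Overtreatment harms are compared between arms only over all accrued patients; rates within the matching index care gap should be added alongside

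*Combined protocol and SAP*

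**What the plan says.** Section 8.3.4 sets the safety population: "We accessed the electronic health records and administrative data of all patients who accrued to this pragmatic trial". It also gives the summary measure: "The rates at which each event occurred (e.g., events per 100 patient-years) were calculated in the pre- and post-index periods by randomized treatment group". Section 10.1.6 adds the comparison and its consequence: "Rates of monitored events will be compared in intervention and usual care clinics, and any significant differences will be promptly reported in writing", to NIH and the IRB. Section 7.1 states that there are no specific halting rules and names the harms of interest as "possible adverse events related to overtreatment (severe hypoglycemia, documented hypotension, abnormal potassium values, etc.) in all randomized clinics".

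No safety section defines a care-gap stratum. Section 9.4.4 says only this: "Trends in safety concerns for subjects will also be followed as indicated by the Data Safety and Monitoring plan". Section 9.4.9 lists the events, and section 9.4.7 concerns moderators of the primary analyses.

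Efficacy is handled differently. Under section 7.3, "inclusion in specific outcome analyses varied by the clinical care gaps that were present at the index visit", and section 9.3 assigns patients to H1–H5 in the same way. The plan gives no event rate, test or power for any safety comparison.

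**The concern.** The tool makes recommendations for each deficit it finds. If it causes overtreatment, a natural place to look is where it prompts: hypoglycemia where A1c is above goal, hypotension where BP is elevated, and abnormal potassium where an ACEI/ARB is suggested. Patients without the matching gap contribute patient-years and background events that those prompts change little. Pooling them pulls the between-arm difference towards zero.

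Benefit and harm are therefore reported on different denominators. A null all-patient safety table could be read as reassurance about the patients in whom H2–H4 claim benefit, although it had limited ability to show harm there.

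**Working it through.** **Plan's own figure.** Section 9.2 prorates 5,766 pilot patients in 17 clinics to 30 clinics: 5,766 × 30/17 = 10,175. This reproduces.

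**Gap shares of the pilot CKD cohort (Table 1)**
- Glucose: 2,066 × (1 − 0.503) = 1,027; 1,027/5,766 = 17.8%.
- ACEI/ARB, stage 3 only as in section 5.1: 3,263 × (1 − 0.594) + 1,470 × (1 − 0.569) = 1,958; 1,958/5,766 = 34.0%.
- BP, one reading not below 130/80: 1 − 0.373 = 62.7%.
- BP, two consecutive readings, taking the pilot within-patient correlation of 0.26 from Table 2: 0.627² + 0.26 × 0.627 × 0.373 = 45.4%.

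**Shares of accrued patients.** Accrual requires at least one gap. The proportion d of CKD patients meeting this is not given, so I assume 0.627 to 1.00. If gaps were independent, d = 1 − (0.822 × 0.660 × 0.546 × 0.492) = 0.85, where 0.492 is the proportion with diagnosed CKD. The share s is the cohort share divided by d:
- Glucose: 17.8% to 28.4%.
- ACEI/ARB: 34.0% to 54.2%.
- BP: 62.7% to 100% on one reading, 45.4% to 72.4% on two.

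**Loss of the absolute rate difference = 1 − s**, if the excess occurs only in gap patients:

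| Harm and gap | d = 1.00 | d = 0.85 | d = 0.627 |
|---|---|---|---|
| Hypoglycemia, glucose | 82% | 79% | 72% |
| Potassium, ACEI/ARB stage 3 | 66% | 60% | 46% |
| Hypotension, BP on two readings | 55% | 47% | 28% |
| Hypotension, BP on one reading | 37% | 27% | 0% |

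**Loss on the ratio scale.** If q is the share of background events falling in gap patients, the all-patient ratio is 1 + q(RR − 1), and the excess ratio lost is 1 − q. At s = 0.18 the loss is 82% with equal background rates, 60% if the gap-patient rate is 3 times higher, 31% if 10 times higher, and 0% if every event is in a gap patient.

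**Power illustration.** Assumptions: background 1 event per 100 patient-years, true RR = 2 in gap patients, mean follow-up 23.5 months (midpoint of the 18 to 29 months in section 5.1), two-sided 0.05, clustering ignored. N and s are matched: 10,175 with d = 1, or 10,175 × 0.627 = 6,380 with d = 0.627. Patient-years per arm are N/2 × 23.5/12 = 9,963 or 6,247, giving 99.6 or 62.5 control-arm events at equal background rates. Then z = ln(RR)/√(1/E₀ + 1/E₁) and power = Φ(z − 1.96).

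| Comparison | E₀ | RR seen | z | Power |
|---|---|---|---|---|
| Glucose, all patients, d = 1 | 99.6 | 1.18 | 1.20 | about 23% |
| Glucose, all patients, d = 0.627 | 62.5 | 1.28 | 1.48 | 32% |
| Glucose, within gap | 17.7 | 2.00 | 2.38 | 66% |
| ACEI/ARB, all patients, d = 1 | 99.6 | 1.34 | 2.21 | 60% |
| ACEI/ARB, all patients, d = 0.627 | 62.5 | 1.54 | 2.67 | 76% |
| ACEI/ARB, within gap | 33.8 | 2.00 | 3.29 | 91% |

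The number of gap patients is the same under either d, so within-gap power does not change.

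If hypoglycemia occurs only in patients with diabetes, at the same rate in and out of the gap, E₀ = 9,963 × 2,066/5,766 × 0.01 = 35.7 and the all-patient ratio is 1 + 0.497 = 1.50. Power is then 46%, against 66% within the gap.

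**The case against.** The strongest reply is that an all-accrued comparison by randomized arm is the standard intention-to-treat safety summary, and that the index gap does not bound exposure. This stands. Recommendations appear at any visit and change with the patient's state (section 6.1.1), so a patient without a gap at index can be prompted later. The tool also suggests titration, which can reach patients already on an ACEI/ARB, who lie outside that gap. Stage 4 patients are outside the ACEI/ARB gap by definition (section 5.1), and an ACEI/ARB start could contribute to hypotension in someone without a BP gap. A gap-only table would miss all of these. The documents themselves do not say that harms arise mainly in the matching gap.

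A second reply is that nothing is lost on the ratio scale when background events are confined to gap patients, because event-free patient-years enlarge both arms equally. The arithmetic is right, but the definitions make that extreme unlikely for two of the harms. About half the pilot patients with diabetes had A1c below 7% and so lie outside the glucose gap. The ACEI/ARB gap excludes patients already on these drugs and those with a recent hyperkalemia code or high potassium, so background potassium events may sit largely outside it.

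A reader might also infer that this comparison is the only safety signal. It is not. Emergency visits, admissions, major CV events and mortality are monitored (section 8.2), pre- to post-index change is examined by arm, and events that come to the team's attention by other routes are recorded (section 8.3.4).

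**Conclusion.** The point holds as a gap in reporting. Harm is compared between arms only over all accrued patients, while benefit is estimated within the matching index gap. If the excess harm is confined to gap patients, the absolute rate difference is reduced by about 72–82% for hypoglycemia and 46–66% for potassium. For hypotension the loss is 0–55%, depending on how the two-reading BP rule plays out. In the illustration, within-gap power is higher in every row. The two would be equal only if all background events fell in gap patients.

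Three stronger readings are tempting and are not supported:
- That the all-patient comparison is an error. It is valid and catches harms the gap tables miss.
- That a doubled harm would go unseen. For potassium, all-patient power is 60–76% under the stated assumptions, so it would more likely than not be detected.
- That all three signals lose half or more. This fails for hypotension over most of its range.

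The sizes rest on 2015–2016 pilot data for ages 18–80, whereas the trial enrolled ages 18–75 with at least one gap. Table 1 rows also match the gap definitions only approximately; for example, the hyperkalemia exclusion is not applied. The any-gap proportion, event rate and rate ratio are assumptions, and ignoring clustering makes all the power figures optimistic.

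**What to change.** In sections 8.3.4 and 9.4.4, keep the all-patient by-arm comparison as primary. Beside it, pre-specify post-index rates by arm for:
- hypoglycemia in the H4 glucose-gap population, and among all patients with diabetes;
- hypotension in the H3 BP-gap population;
- potassium events in the H2 ACEI/ARB-gap population.

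Put these in the final safety report and in any safety reviews still to come. Section 8.3.4 describes past summaries as already presented, so those cannot change.

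The cost is SAP wording and a few table rows, since index-gap flags and safety events are already held for all patients. The gap tables will have fewer events, will add comparisons, and will miss patients prompted or titrated outside their index gap. They should therefore be labeled supplementary, and the all-patient table should stay.

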8.3.5 ADVERSE EVENT REPORTING

According to the HealthPartners Institute IRB policies, investigators must report the specified adverse events or issues to the IRB as soon as possible, but in no event later than 10 working days after the investigator first learns of the event. Investigators or the project team must report possible problems or issues with the research to the IRB Office in writing using the Unanticipated Problem/Serious Adverse Event Form. The written report should contain the following: Detailed information about the event or issue, including relevant dates; Any corrective and preventative actions, planned or already taken, to ensure that the issue or problem is corrected and will not occur again; An assessment of whether any subjects or others were placed at risk as a result of the event or suffered any harm (e.g., physical, social, financial, legal or psychological) and any plan to address these consequences.

8.3.6 SERIOUS ADVERSE EVENT REPORTING

The study investigator shall complete a written report and submit to the study sponsor and to the reviewing Institutional Review Board (IRB) as soon as possible, but in no event later than 10 working days after the investigator first learns of the event.

8.3.7 REPORTING EVENTS TO PARTICIPANTS

Participating clinics will be informed of AEs and SAEs through communication with the clinic and healthcare group leadership and providers. Although unlikely, if specific patients are affected or at risk, they will be contacted through their routine patient communication channels and through their providers.

8.3.8 EVENTS OF SPECIAL INTEREST

Not applicable

8.3.9 REPORTING OF PREGNANCY

Pregnancy is an exclusion criteria for the study. However, reporting is not warranted as there is no direct harm anticipated from the study.

8.4 UNANTICIPATED PROBLEMS

8.4.1 DEFINITION OF UNANTICIPATED PROBLEMS (UP)

The Office for Human Research Protections (OHRP) considers unanticipated problems involving risks to participants or others to include, in general, any incident, experience, or outcome that meets ALL of the following criteria:

- Unexpected in terms of nature, severity, or frequency given (a) the research procedures that are described in the protocol-related documents, such as the IRB-approved research protocol and

informed consent document; and (b) the characteristics of the participant population being studied;

- Related or possibly related to participation in the research (“possibly related” means there is a reasonable possibility that the incident, experience, or outcome may have been caused by the procedures involved in the research); and
- Suggests that the research places participants or others at a greater risk of harm (including physical, psychological, economic, or social harm) than was previously known or recognized.

8.4.2 UNANTICIPATED PROBLEM REPORTING

The investigator will report UPs to the reviewing IRB and to HealthPartners Institute. The UP report will include the following information:

- Protocol identifying information: protocol title and number, PI’s name, and the IRB project number;
- A detailed description of the event, incident, experience, or outcome;
- An explanation of the basis for determining that the event, incident, experience, or outcome represents an UP;
- A description of any changes to the protocol or other corrective actions that have been taken or are proposed in response to the UP.

To satisfy the requirement for prompt reporting, UPs will be reported using the following timeline:

- UPs that are SAEs will be reported to the IRB and to the study sponsor within 5 days of the investigator becoming aware of the event.
- Any other UP will be reported to the IRB and the study sponsor within 10 working days of the investigator becoming aware of the problem.
- All UPs should be reported to appropriate institutional officials (as required by an institution’s written reporting procedures), the supporting agency head (or designee), and the OHRP within 1 month of the IRB’s receipt of the report of the problem from the investigator.

8.4.3 REPORTING UNANTICIPATED PROBLEMS TO PARTICIPANTS

Participating clinics will be informed of UPs through communication with the clinic and healthcare group leadership and providers. Although unlikely, if specific patients are affected or at risk, they will be contacted through their routine patient communication channels and through their providers.

9 STATISTICAL CONSIDERATIONS

9.1 STATISTICAL HYPOTHESES

Hypothesis 1: Among patients with antecedent eGFR evidence of stage 3-4 CKD, those with an index visit at a CKD-CDS intervention clinic will have significantly higher rates of provider-diagnosed CKD in the 18 months after the date of the index visit, compared with similar patients with an index visit at a UC clinic.

Hypothesis 2: Among patients with antecedent eGFR evidence of stage 3-4 CKD who also have diagnosed hypertension or UMACR ≥ 30 mg/g, those with an index visit at a CKD-CDS intervention clinic will have significantly higher rates of ACEI or ARB use 18 months after the date of the index visit, compared with similar patients with an index visit at a UC clinic.

Hypothesis 3: Among patients with antecedent eGFR evidence of stage 3-4 CKD who have diagnosed hypertension, those with an index visit at a CKD-CDS intervention clinic will have significantly higher rates of recommended BP control 18 months after the index visit date, compared with similar patients with an index visit at a UC clinic.

Hypothesis 4: Among patients with antecedent eGFR evidence of stage 3-4 CKD who also have diagnosed diabetes at an index visit, those with an index visit at a CKD-CDS intervention clinics will have significantly higher rates of recommended glucose control 18 months after the date of the index visit, compared with similar patients with an index visit at a UC clinic.

Hypothesis 5: Among patients with eGFR laboratory evidence of stage 3b (eGFR 30-44 ml/min/1.73 m²) CKD and UMACR >30 mg/g, or patients with stage 4 (eGFR 15-29 ml/min/1.73 m²) CKD, those with an index visit at a CKD-CDS intervention clinic will have significantly higher rates of consultation with nephrology 18 months after index visit, compared with similar patients with an index visit at a UC clinic.

The operational definitions of the outcomes associated with Hypothesis 1-5 are summarized below.

outcome	description	operational definition
H1: CKD recognition	CKD documented in the electronic health record	ICD-10 codes N18.3, N18.4, N18.5, N18.6, N18.9 at an inpatient or outpatient encounter, or added to the problem list, on index date through 18 months post-index
H2: ACEI / ARB use	ACEI / ARB current post-index	ACEI / ARB orders with start date or end date on index date through 18 months post-index
H3: Blood pressure control	post-index BP at goal	in 18 months post-index, average of up to two most recent SBP<130; and average up to two most recent DBP<80
H4: Glucose control	post-index A1c at goal	most recent A1c<7% in 1 to 18 months post-index
H5: Nephrology referral	nephrology referral	referral to or completed visit with nephrologist, on index date through 18 months post-index

